8.3.4. Subject Replacement

Subjects will be replaced at Ultragenyx's discretion only if they have not received study drug. Subjects will not be replaced if they have received any study drug.

8.4. Informed Consent

Informed consent must be obtained from the patient before performing any study-related procedures.

In the event that a subject is rescreened (Section [8.5](#)), a new informed consent form (ICF) must be signed.

8.5. Screening Requirements

All screening evaluations specified in [Table 4](#), [Table 5](#), and [Table 6](#) must be completed and reviewed to confirm eligibility. The Investigator will maintain a screening log to record details of all subjects screened and to confirm eligibility or record reasons for screening failure, as applicable.

At the Screening Visit for SAD cohorts and ISV for DB-RD cohorts, informed consent will be obtained, and general medical information (ie, demographics, general medical history, and GSD III specific medical history), a complete physical exam, vital signs, anthropometrics, concomitant medications, and dietary information will be collected. Subjects will also be screened for hepatitis B and C. Several laboratory assessments, as outlined in [Table 4](#), [Table 5](#), and [Table 6](#), will be collected during screening.

Subjects in the SAD cohorts who complete the 90-day Follow-up Period can elect to enter OL-RD cohorts. These subjects will complete an abbreviated rescreening for participation in the OL-RD cohorts, occurring over the course of at least 3 weeks prior to redosing; eligibility for additional dosing in the OL-RD cohorts (ie, rescreening) can be combined with assessments at the SAD Day 90 Visit. Informed consent for participation in the OL-RD cohorts must be signed prior to rescreening.

Rescreening for subjects who previously failed screening is permissible on a case-by-case basis. Each case should be discussed with the Medical Monitor. If a subject is rescreened for the DB-RD cohorts, the subject will still be required to complete up to 6 weeks of nutrition stabilization during screening. Subjects who undergo rescreening for DB-RD cohorts may not need to repeat the imaging assessments.

9. INTERVENTION(S)

An overview of all interventions, including the IP, premedications, and rescue medications are provided in [Table 12](#).

Table 12: Study Investigational Product, Premedication, and Rescue Medication

	Intervention ^a					
	UX053	Placebo	Paracetamol/ acetaminophen or ibuprofen ^b	H1 blocker; cetirizine or equivalent	H2 blocker; famotidine or equivalent	Dexamethasone or equivalent ^c
Dose Formulation	Ampule	Ampule	Tablet	Tablet	Tablet	Ampule
Unit Dose Strength(s) / Dosage Level(s)	0.05, 0.10, and 0.20, mg/kg single dose during in SAD cohorts and Q2W or Q4W in RD cohorts ^d	-	500 mg (paracetamol /acetaminophen); 400-800 mg (ibuprofen)	10 mg for cetirizine	20 mg for famotidine	10 mg for IV dexamethasone
Route of Administration	IV infusion	IV infusion	Oral	Oral	Oral	IV infusion
Use	Experimental	Placebo	Premedication ^e	Premedication ^e	Premedication ^e	Rescue medication, or premedication for subsequent infusions if used as rescue medication previously

^a Regardless of assigned treatment (UX053 or placebo), all subjects in DB-RD cohorts will also be asked to maintain a diet based on expert recommendations for adults with GSD III throughout the study ([Table 2](#)).

^b Paracetamol/acetaminophen is preferred over ibuprofen.

^c Dexamethasone should be the first-in-line rescue medication; alternative or additional rescue medications are allowed, if necessary, at the discretion of the Investigator. The Medical Monitor must be notified if any rescue medication is used.

^d Additional cohort(s) at dose levels between 0.05 mg/kg to 0.30 mg/kg may also be included pending review of safety data.

^e Premedications will be administered to all subjects, including subjects receiving placebo. At the discretion of the Investigator, with input from Ultragenyx and the DMC, and based on the emerging safety profile of UX053, additional premedications and rescue medications may be used to reduce the risk and severity of immune reactions in RD cohorts. Premedication and rescue medication selection will be based on the nature of the reactions being observed and the risks of such medications in patients with GSD III.

DB, double-blind; DMC, Data Monitoring Committee; GSD, Glycogen Storage Disease; IV, intravenous; Q2W, every 2 weeks; Q4W, every 4 weeks; RD, Repeat Dose; SAD, Single Ascending Dose.

9.1. UX053

UX053 consists of an mRNA encoding full-length, human GDE encapsulated in an LNP.

CCI

Both UX053 and placebo will be diluted prior administration such that the concentration of components, including sucrose, is identical. The final concentration (for both UX053 and placebo) will be CCI

Additional information on physical and chemical properties of UX053 are provided in the IB.

UX053 is supplied in a frozen sterile solution in a vial. UX053 should be stored in a freezer, set to maintain CCI °C, protected from light. UX053 is manufactured, packaged and labelled according to current Good Manufacturing Practices (GMP).

9.1.1. Premedications

The study site will supply premedications that will be obtained locally. Subjects will receive premedication at least 1 hour prior to the infusion, consisting of oral paracetamol/acetaminophen (500 mg) or ibuprofen (400 to 800 mg), an H2 blocker (eg, famotidine 20 mg or equivalent dose of another H2 blocker), and an H1 blocker (eg, cetirizine 10 mg or equivalent dose of another H1 blocker). For the premedication, paracetamol/acetaminophen is preferred over ibuprofen. At the discretion of the Investigator, with input from Ultragenyx and the DMC, and based on the emerging safety profile of UX053, additional premedications and rescue medications may be used to reduce the risk and severity of immune reactions in RD cohorts. Premedication and rescue medication selection will be based on the nature of the reactions being observed and the risks of such medications in patients with GSD III. If a subject develops an IRR that meets diagnostic criteria for anaphylaxis (Section 8.3.3), should be administered as initial rescue medication. For all other hypersensitivity reactions \geq Grade 2 in severity suspected to be due to immune activation, dexamethasone should be the initial rescue medication (Section 9.5). The Medical Monitor must be notified if any rescue medication is used. If dexamethasone (or equivalent) is used as a rescue medication, premedication with dexamethasone (or equivalent) should be considered for that subject's subsequent infusions after discussion with the Medical Monitor. Section 8.3.2 provides subject-level redosing criteria, stopping criteria, and additional instructions on how to proceed in the event of an IRR.

9.1.2. Preparation and Administration

For detailed preparation and administration information, refer to the Pharmacy Manual. Prior to each infusion, the amount of study drug will be determined based on subject weight (in kg). The volume of study drug calculated to deliver the correct dose will be withdrawn from the vial. Study drug will be diluted and transferred to an infusion bag as a final dose. Undiluted UX053 must never be infused.

Study drug is administered as an IV infusion over the course of at least 4 hours, with a slower rate of infusion for the first hour to minimize the risk of hypersensitivity or anaphylactoid-type reactions. The infusion rate schedule may be slowed to minimize the risk of IRRs in individual

subjects. Study drug is administered once in the SAD cohorts and either Q2W or Q4W in the RD cohorts.

9.1.3. Clinical Observation and Supportive Care

Subjects will stay overnight onsite on for all dosing visits for safety and PK assessments. If a subject develops an IRR that meets diagnostic criteria for anaphylaxis (Section 8.3.3), epinephrine should be administered as initial rescue medication. For all other hypersensitivity reactions \geq Grade 2 in severity suspected to be due to immune activation, dexamethasone should be the initial rescue medication; alternative or additional rescue medications are allowed, if necessary, at the discretion of the Investigator. The Medical Monitor must be notified if any rescue medication is used. If dexamethasone (or equivalent) is used as a rescue medication, premedication with dexamethasone (or equivalent) should be considered for that subject's subsequent infusions after discussion with the Medical Monitor. Section 8.3.2 provides subject-level redosing criteria, stopping criteria, and additional instructions on how to proceed in the event of an IRR. Table 7 and Table 8 show the schedule for vital signs and PK assessments, respectively, occurring before, during, and after study drug infusion.

9.1.4. Guidance on Communication and Seeking Immediate Medical Attention

Subjects should inform their primary care provider of their participation in the UX053-CL101 clinical trial. Communication between the subject's primary care provider and study Investigators is strongly encouraged, and study Investigators should share visit summaries and hospital discharge summaries with the subject's primary care provider. Subjects should contact their primary care provider for routine care outside the management of GSD III.

At any time during the study, subjects should contact the Investigator if they notice any changes in their health or any other symptoms that cause the subject distress. Based on the clinical assessment and judgement of the study Investigator, the subject may be referred to their primary care physician, to seek treatment in an emergency room, or to contact local emergency services.

At any time during the study, subjects should seek immediate medical attention and notify the Investigator if they develop any of the following signs or symptoms:

- Signs of a severe hypersensitivity reaction, such as generalized urticaria, angioedema, respiratory distress, or anaphylaxis
- Jaundice
- Unusual bleeding or bruising
- Altered mental status, seizure, syncope, dizziness, or presyncope
- Severe chest or abdominal pain
- Blood sugar below 54 mg/dL (3 mmol/L) accompanied by symptoms of neuroglycopenia (dizziness, weakness, drowsiness, confusion, or altered mental status)

9.1.5. Dose Modification

If a subject develops a TEAE/serious TEAE \geq Grade 3 that is considered by the Investigator to be related to study drug or an intolerable TEAE in the RD cohorts, subject-level dose reductions are allowed in consultation with the Medical Monitor, as outlined in the guidance provided in the Pharmacy Manual. At any time, the DMC may recommend discontinuation of dosing for an individual subject or for all subjects. At any time, Ultragenyx may modify or discontinue dosing for an individual subject or for all subjects.

Dose levels for each cohort, in either the SAD or RD cohorts, may be reduced and/or higher dose cohorts may not be initiated, depending on safety and PD findings from prior cohorts, as determined by Ultragenyx (with input from the DMC for the RD cohorts).

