At any time Ultragenyx may decide not to initiate a planned dose cohort. Dose levels for each cohort may be altered depending on safety, PK, and/or PD findings from prior cohorts. If needed to evaluate safety and dose-response relationships, additional cohorts may be added to test doses up to 0.30 mg/kg or additional subjects may be added to a cohort at the discretion of Ultragenyx to further characterize safety, PK, and PD effects, with input from the DMC. In every case, the safety of a single dose will be evaluated prior to repeat doses at the same dose level.

If a subject in an RD cohort develops a treatment-emergent adverse event (TEAE)/serious TEAE \geq Grade 3 that is considered by the Investigator to be related to study drug or an intolerable TEAE, subject-level dose reductions are allowed in consultation with the Medical Monitor. Ultragenyx will notify the DMC immediately if any subject experiences an event that satisfies subject-level stopping criteria (Section [8.3.2](#)) or study-level stopping criteria (Section [8.3.3](#)).

Glucose and Nutrition Data Collection by Study Subjects

At the Screening Visit for the SAD cohorts and ISV for the DB-RD cohorts, all subjects will receive CGM and handheld glucometer (HHG) devices and will be trained on the proper use of

these devices. Subjects will also be trained on completion of the nutrition diary During screening. Subjects entering the OL-RD cohorts do not need to be retrained if compliance was acceptable during participation in the SAD cohorts. When CGM data is being collected, all subjects will connect their CGM and HHG devices to a study-provided laptop weekly and upload CGM and HHG data. At remote visits, in conjunction with assessments performed by a home health nurse, the site will contact subjects by telephone or videoconference to confirm the CGM device is properly in use and data was uploaded; answer any questions regarding or help troubleshoot (if necessary) CGM device use; and review CGM data, HHG data (when applicable), and nutrition diary entries; outside of scheduled visits, these telephone calls will occur as needed. At in-clinic visits, a conversation between the site and the subject should occur to ensure CGM compliance and troubleshoot if needed.

Drug Administration, Dose Interval, and Blinding

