8.3.2. Subject-level Redosing and Stopping Criteria

At any time after the first dose of study drug, if a marked increase in transaminases (ie, $> 2x$ the subject's baseline value and $3x$ ULN) is observed, liver enzymes, bilirubin, and INR should be obtained again within 48 to 72 hours. Study drug should not be re-administered unless the following criteria are met:

- If a significant rise in ALT occurs after the prior dose, ALT should show a decreasing trend toward the subject's baseline value
- Total bilirubin is within normal limits
- Platelets are within normal limits
- INR is within normal limits

Additionally, subjects who meet any of the following criteria will not be redosed:

- Subjects who develop new or worsening symptoms of liver disease (including new or worsening hepatomegaly) along with any increase in transaminase levels
- Subjects who require any blood product administration (eg, packed red blood cells, platelet, fresh frozen plasma) for management of consumptive coagulopathy

- Subjects who develop an ALT level that is $\geq 8x$ ULN and $> 2x$ the subject's baseline value in the absence of an alternative explanation

If a subject develops an IRR that meets diagnostic criteria for anaphylaxis ([Table 11](#)), epinephrine should be administered as initial rescue medication. For all other hypersensitivity reactions \geq Grade 2 in severity suspected to be due to immune activation, dexamethasone should be the initial rescue medication. The Medical Monitor must be notified if any rescue medication is used.

If dexamethasone (or equivalent) is used as a rescue medication, premedication with dexamethasone (or equivalent) should be considered for that subject's subsequent infusions after discussion with the Medical Monitor.

In the event of an IRR, action outlined in [Table 10](#) should be implemented based on the level of severity. Ultragenyx will confer with the DMC whenever subject- or study-level stopping criteria are potentially met.

Table 10: Action in the Event of an Infusion-Related Reaction

IRR CTCAE Severity	Action
Grade 1 (Mild)	The infusion may be slowed or interrupted temporarily and resumed at the original speed

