Grade 2 (Moderate)	The infusion should be interrupted. The post-infusion complement and cytokine labs should be obtained within 1 hour of the start of the reaction. The subject should be closely monitored, and supportive care should be provided. Dexamethasone 10 mg IV (or equivalent) should be administered. Additional treatment, including a complement inhibitor (such as eculizumab) may be considered. The infusion may be restarted at half the rate after symptomatic treatment and resolution of the reaction. If the subject has IRR following resumption at the lower rate, stop the infusion.
Grade ≥ 3 (Severe, Life-threatening, Death)	The infusion should immediately be terminated. The post-infusion complement and cytokine labs will be obtained within 1 hour of the start of the reaction. The subject should be closely monitored, and supportive care should be provided. Dexamethasone 10 mg IV (or equivalent) should be administered. Additional treatment, including a complement inhibitor (such as eculizumab) may be considered. The subject will not be redosed.

CTCAE, Common Terminology Criteria for Adverse Events; IRR, infusion-related reaction; IV, intravenous.

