8.3.3. Study Stopping Criteria

Study enrollment and any further administration of study drug for subjects already enrolled, will be paused and the DMC and regulatory authorities will be notified if, at any time during the study, any of the criteria listed below occur after UX053 administration:

- Death of a subject
- Any serious TEAE with a severity \geq Grade 3 that is assessed as related to study drug or study procedures by the Investigator or Ultragenyx
- Any TEAE with a severity \geq Grade 3 affecting the cardiopulmonary, renal, or neurological systems, regardless of relationship to study drug, pending a DMC safety review

- Anaphylaxis, as defined by the National Institute of Allergy and Infectious Diseases/Food Allergy and Anaphylaxis Network (NIAID FAAN) criteria ([Table 11](#)), pending a DMC safety review
- Increases in ALT or AST $> 2x$ from Baseline and $> 3x$ the ULN, accompanied by total bilirubin $> 2x$ ULN or INR > 1.5 , without findings of cholestasis (defined as serum ALP activity $< 2x$ ULN) and in the absence of a plausible alternate explanation
- Increases in serum concentrations of ALT or AST $> 2x$ from Baseline and $> 3x$ ULN with the appearance of fatigue, nausea, vomiting, right upper quadrant pain or tenderness, fever, rash, or eosinophilia ($> 5\%$ of total leukocytes)
- 3 subjects develop platelet counts $< 50,000$ per mm³ (or thrombocytopenia \geq Grade 3 in severity)
- 3 subjects develop INR > 1.5 (or INR increase \geq Grade 2 in severity)

In addition to the above criteria, the DMC may at any time recommend dose reduction or discontinuation of dosing for an individual subject or for all subjects (Section [9.1.5](#)). Regulatory authorities will be notified immediately if the study stopping criteria are met and study enrollment or dosing is halted.

Table 11: Clinical Criteria for Diagnosing Anaphylaxis

Anaphylaxis is highly likely when any one of the following 3 criteria are fulfilled:

1. Acute onset of an illness (minutes to several hours) with involvement of the skin, mucosal tissue, or both (eg, generalized hives, pruritus or flushing, swollen lips-tongue-uvula)
 
AND AT LEAST ONE OF THE FOLLOWING
 
a. Respiratory compromise (eg, dyspnea, wheeze-bronchospasm, stridor, reduced PEF, hypoxemia) b. Reduced BP or associated symptoms of end-organ dysfunction (eg, hypotonia [collapse], syncope, incontinence)

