11.4. Safety Analyses

Safety variables including all AEs, SAEs, TEAEs, serious TEAEs, related TEAEs, safety laboratory assessments (full list available in [Appendix 3](#)), vital signs, weight, physical examination, clinical laboratory evaluations, and ECGs will be summarized for all subjects throughout the study and by treatment and cohort. Incidence and severity of IRRs and hypersensitivity reactions will also be summarized for all subjects throughout the study and by treatment and cohort. All AEs occurring from the onset of the study treatment infusion, and within 4 hours following the end of the infusion, regardless of the Investigator's assessment of whether or not the event was related to study drug administration will be considered an IRR.

All AEs will be coded according to the Medical Dictionary for Regulatory Activities (MedDRA) Version 23.0. The frequency and severity of all TEAEs, SAEs, and clinically relevant laboratory and ECG abnormalities will be reported by System Organ Class (SOC), by preferred term, and by relationship to study drug. All AEs reported with onset after the first dose of study drug (ie, TEAEs) will be included in the analysis. All SAEs will also be reported by relationship to study drug as reported by Investigator, seriousness, and outcome. For all AEs, SAEs, and treatment-related AEs, SAEs, the percentage of subjects who experienced at least 1 occurrence of the given event will be summarized for all subjects in the SAD cohorts and by treatment and cohort for the RD cohorts. Data summaries, listings, and narratives will be provided for subjects who died, discontinued treatment or withdrew from study due to an AE, or experienced SAEs, and any study procedure-related AEs.

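### In the repeat-dose cohorts, a related Grade ≥ 3 infusion-related reaction meets two protocol rules that disagree on redosing, and no passage says which one governs

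*Protocol*

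**What the plan says.** **The ban.** Protocol Section 8.3.2 says that after an IRR the Table 10 action "should be implemented based on the level of severity". In the Grade ≥ 3 row the infusion is terminated, and the entry ends: "The subject will not be redosed". The row gives no exception and no role for the Medical Monitor.

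**The permission.** Section 9.1.5 covers RD subjects who have a TEAE or serious TEAE of Grade 3 or higher that the Investigator considers related, or an intolerable TEAE. For them "subject-level dose reductions are allowed in consultation with the Medical Monitor, as outlined in the guidance provided in the Pharmacy Manual". Section 7.1 has the same rule for an event "related to study drug or an intolerable TEAE, subject-level dose reductions are allowed in consultation with the Medical Monitor", without the Pharmacy Manual, and the synopsis repeats it. SAP Section 3 restates it with the manual.

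**The only explicit definition of an IRR.** It is in Section 11.4, Safety Analyses: "All AEs occurring from the onset of the study treatment infusion, and within 4 hours following the end of the infusion" count as IRRs, whatever the Investigator's view of causality. Table 10 does not cite this definition.

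**The pointers.** Sections 7.1, 7.1.4, 9.1.1, 9.1.3 and 9.5 each refer the reader to 8.3.2 for redosing and stopping criteria and for handling an IRR. Section 9.1.5 does not.

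**The concern.** A reduced dose is still a further dose. For a related Grade ≥ 3 IRR, one section forbids any further dose and another permits a lower one after consultation. Neither mentions the other.

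Section 5.4.1 lists hypersensitivity, which includes IRRs, first among the potential risks of UX053. Whether to dose again after a severe reaction is a key subject-level decision in a first-in-human trial, and it should not depend on which section a site opens. A reader who goes to the section titled Dose Modification finds the permission and a reference to the Pharmacy Manual, but nothing that leads to Table 10.

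Inconsistent handling would also blur the exposure data. A double-blind cohort has 4 subjects randomized 3:1, so 3 receive UX053. One active subject handled differently is 1/3, or 33%, of that cohort's repeat-dose exposure.

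**Working it through.** The plan states no figure on this point to reproduce. The check compares trigger, scope and action, and then looks for a rule of precedence.

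| | Table 10 (8.3.2) | Sections 7.1 and 9.1.5, synopsis |
|---|---|---|
| Trigger | IRR of Grade ≥ 3 | TEAE or serious TEAE of Grade ≥ 3 judged related, or an intolerable TEAE |
| Scope | Any subject with such an IRR | RD cohorts |
| Action | No further dose | Reduced dose allowed after consulting the Medical Monitor |
| Exception for the other rule | None | None |

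**Step 1: can one event meet both triggers?** Yes. Take an RD subject with a Grade 3 IRR that the Investigator calls related. It is an IRR of Grade ≥ 3, so Table 10 applies. It is a related TEAE of Grade ≥ 3, so the permission applies. This holds however an IRR is defined, so it does not rely on the Section 11.4 window.

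**Step 2: are the actions compatible?** Only in one direction. Giving no further dose satisfies both texts. Giving a reduced dose with the Medical Monitor's agreement is allowed by 9.1.5 and forbidden by Table 10.

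**Step 3: does any passage set precedence?** None was found.
- The pointers to 8.3.2 say where the IRR instructions are. They do not say that those instructions override the permission.
- In Section 7.1 the sentence after the permission requires immediate DMC notification when stopping criteria are met. It does not say that the permission then lapses.
- Section 8.3.2 has the sponsor confer with the DMC when stopping criteria may be met. It does not mention 9.1.5.

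**Step 4: where can the conflict arise?** Only where another dose is planned.
- SAD: 1 dose, so 1 − 1 = 0 infusions followed by another.
- DB-RD: 5 doses, so 5 − 1 = 4.
- OL-RD: 4 doses, so 4 − 1 = 3.

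**Step 5: does it affect reported results?** SAP Section 8 says the study terminated after 4 subjects in Cohort 1S and 4 in Cohort 2S, and that only analyses of those cohorts will be provided. Both are single-dose cohorts.

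**The case against.** The best defence is that Table 10 is the specific rule and the dose-reduction text the general one, so Table 10 governs. The repeated pointers to 8.3.2 support this. The permission is conditional, nothing orders a redose, and a Medical Monitor and DMC would have to overlook 8.3.2 before a barred dose was given. Much of this stands. It makes the defect a narrow one, a ban against a conditional permission. It does not remove it, because the reader must supply the precedence and 9.1.5 lacks even the pointer. The Pharmacy Manual was not available, so it may contain an exception. If so, the protocol does not show it.

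A reader might infer more than the documents support:

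- **That sites have two opposite orders.** They do not, since withholding the dose complies with both.
- **That the study pause in Section 8.3.3 also contradicts the permission.** That criterion covers a serious TEAE of Grade ≥ 3 "that is assessed as related to study drug or study procedures by the Investigator or Ultragenyx". A study-wide pause and a later decision about one subject can follow in sequence. Section 8.3.3 itself cites 9.1.5 when it says that the DMC may recommend a reduction or discontinuation for an individual.
- **That every severe event in the Section 11.4 window, including unrelated hypoglycemia, falls under both rules.** Section 11.4 defines how events are summarized, and Table 10 does not cite it. Table 10's instruction to terminate the infusion also fits poorly with an event hours after the infusion has ended. An unrelated event that is not intolerable is outside the trigger in 7.1 and 9.1.5, so no second rule applies to it.
- **That the overlap is 40 hours (5 × 8) for DB-RD and 32 hours (4 × 8) for OL-RD.** The 8 hours are an infusion of at least 4 hours plus 4 hours after it. No dose follows the last infusion, so even on that window the totals are at least 4 × 8 = 32 and 3 × 8 = 24 hours. Hours of window say nothing about how often such reactions occur.

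**Conclusion.** The inconsistency is real and can be read from the current text. In the RD cohorts, a related Grade ≥ 3 IRR is barred from redosing by Table 10 and eligible for a reduced dose under Section 7.1, the synopsis and Section 9.1.5. No exception or order of precedence is stated.

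Its reach is limited to the first 4 of 5 DB-RD infusions and the first 3 of 4 OL-RD infusions, and to events that are related and of Grade ≥ 3. The documents give no rate for such events, so no expected number can be stated.

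The conclusion assumes that a dose reduction means a further dose at a lower level and that no unseen site document sets the precedence. It concerns the clarity of a safety instruction. The SAP will report only Cohorts 1S and 2S, so no reported analysis changes. It should be corrected before any repeat dosing under this text or any reuse of it. It is not a reason to doubt the single-dose results.

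**What to change.** Reconcile the passages:

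1. In the synopsis, Section 7.1 and Section 9.1.5, add a cross-reference to Section 8.3.2 and Table 10 beside the dose-reduction sentence, and state the order of precedence, so that a related Grade ≥ 3 IRR has one outcome.
2. State in Table 10 or Section 11.4 whether the time window is only a tabulation rule or also triggers the Table 10 actions.
3. Check that the Pharmacy Manual agrees with the reconciled wording, and use the same reference to it in 7.1 and 9.1.5.

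Which rule prevails is for the sponsor and DMC. The cost is a few sentences in an amendment and a note to sites, with no added visits, assessments or subjects.
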